5.4 Duration of Therapy

In the absence of treatment delays due to adverse event(s), treatment may continue for up to 2 years or until one of the following criteria applies:

- Disease progression warranting alternative systemic therapy,
- Intercurrent illness that prevents further administration of treatment,
- Patient decides to withdraw from the study.
- General or specific changes in the patient's condition render the patient unacceptable for further treatment in the judgment of the investigator.
- In patients with documented disease progression, treatment with MK-3475 can continue until one of the above occurs or until there is an increase in tumor burden of 25% or more following initial confirmation of progression.
- Unacceptable adverse event(s), including:
 - Any Grade 2 drug-related uveitis or eye pain or blurred vision that does not respond to topical therapy and does not improve to Grade 1 severity within the re-treatment period OR requires systemic treatment.
 - Grade 3 drug-related autoimmune or inflammatory event including uveitis, pneumonitis, diarrhea, colitis, neurologic adverse events, hypersensitivity reaction, or infusion reaction of any duration requires discontinuation.
 - Any Grade 3 or 4 drug-related laboratory imbalance or electrolyte abnormality, not associated with underlying organ pathology and that do not require treatment except for electrolyte replacements do not require treatment discontinuation, with the following exceptions with approval of the Principal Investigator:
 - Hypophysitis or pan-hypopituitarism any grade should discontinue treatment.
 - Grade 4 amylase or lipase abnormalities that are not associated with DM, associated liver or gall bladder inflammation clinical manifestations of pancreatitis and which decrease to <Grade 4 within 1 week of onset may stay

on study.

- Any drug-related liver function test (LFT) abnormality that meets the following criteria requires discontinuation: Grade 3 AST or ALT ($>5 \times$ ULN) and total bilirubin $>3 \times$ ULN.
- Grade 3 drug-related thrombocytopenia >7 days or associated with bleeding requires discontinuation.
- Any patient requiring systemic steroid or other immunosuppressive treatment.
- For patients with skin-only toxicity, when symptoms improve to Grade 1 or less, steroid taper should be started and continued over no less than 4 weeks. Discontinue MK-3475 if unable to reduce corticosteroid dose for irAEs to ≤ 10 mg. MK-3475 treatment may be restarted and the dose modified as specified in the protocol.
- Patients with peripheral thyroiditis and no other autoimmune/inflammatory event may be restarted after a short course of steroids on a stable replacement regimen.
- Any dosing interruption lasting >12 weeks with the following exceptions:
 - Dosing interruptions >12 weeks that occur for non-drug-related reasons may be allowed if approved by the Principal Investigator. Prior to re-initiating treatment in a subject with a dosing interruption lasting >12 weeks, the Principal Investigator must be consulted.
 - Tumor assessments should continue as per protocol even if dosing is interrupted.

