5.7 Criteria to Resume Treatment

For non-autoimmune or inflammatory events, patients may resume treatment with study drug when the drug-related AE(s) resolve to Grade ≤ 1 or baseline value, with the following exceptions:

- Patients may resume treatment in the presence of Grade 2 fatigue.
- Patients with baseline Grade 1 AST/ALT or total bilirubin who require dose delays for reasons other than a 2-grade shift in AST/ALT or total bilirubin may resume treatment in the presence of Grade 2 AST/ALT OR total bilirubin.
- Patients with combined Grade 2 AST/ALT AND total bilirubin values meeting study parameters outlined in Section 5.4 should have treatment permanently discontinued.
- Non-drug-related toxicity including hepatic, pulmonary toxicity, diarrhea, or colitis, must have resolved to baseline before treatment is resumed.
- Drug-related endocrinopathies (not including drug-related adrenal insufficiency or hypophysitis) adequately controlled with only physiologic hormone replacement may resume treatment after replacement correction and clinically stable regimen.

If the criteria to resume treatment are met, the patient should restart treatment no sooner than the next scheduled time point per protocol. However, if the treatment is delayed past the next scheduled time point per protocol, the treatment should resume at the earliest convenient point that is within the 12 week delay period.

If treatment is delayed >12 weeks, the patient must be permanently discontinued from study therapy, except as specified in [Section 5.4](#) (Duration of Therapy).

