	Grade 3-4	
Withhold MK-3475
 
Discontinue if unable to reduce corticosteroid dose to <10 mg per day prednisone equivalent within 12 weeks of toxicity
	
 • In patients with Grade 3 enterocolitis, MK-3475 will be permanently discontinued and treatment with systemic corticosteroids should be initiated at a dose of 1 to 2 mg/kg/day of prednisone or equivalent. When symptoms improve to Grade 1 or less, corticosteroid taper should be started and continued over at least 1 month. 
For Grade 3-4 diarrhea (or Grade 2 diarrhea that persists after initial steroid treatment),
 
 • Rule out bowel perforation. Imaging with plain films or computed tomography (CT) can be useful. • Consider consultation with gastroenterologist and confirmation biopsy with endoscopy. • Treat with intravenous (IV) steroids (methylprednisolone 125 mg) followed by high-dose oral steroids (prednisone 1-2 mg/kg once per day or dexamethasone 4 mg every 4 hours). When symptoms improve to grade 1 or less, steroid taper should be started and continued over no less than 4 weeks. Taper over 6-8 weeks in patients with diffuse and severe ulceration and/or bleeding. • If IV steroids followed by high-dose oral steroids does not reduce initial symptoms within 48-72 hours, consider treatment with infliximab at 5 mg/kg once every 2 weeks. Discontinue infliximab upon symptom relief and initiate a prolonged steroid taper over 45-60 days. If symptoms worsen during steroid reduction, initiate a retapering of steroids starting at a higher dose of 80 or 100 mg followed by a more prolonged taper and administer infliximab. CAUTION: infliximab is contraindicated in patients with bowel perforation or sepsis^b. • If symptoms persist despite the above treatment a surgical consult should be obtained. 	
peritoneal signs and ileus). In symptomatic patients, infectious etiologies should be ruled out, and if symptoms are persistent and/or severe, endoscopic evaluation should be considered.
	

Event(s)	CTCAE v5.0 Grade	Management / Next Dose for MK-3475	Action / Supportive Care Guidelines	Symptoms ^a	Differential Diagnosis

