Endocrine events 
 • Hyperthyroidism • Hypophysitis • Hypopituitarism • Hypothyroidism • Thyroid disorder • Thyroiditis 	Grade 1-2	No change in dose	
 • Monitor thyroid function or other hormonal level tests and serum chemistries more frequently until returned to baseline values. 	Symptoms may include (but not limited to): 
 • Abdominal pain • Abnormal thyroid function tests and/or serum chemistries (Thyroid-stimulating hormone increased [decreased], Free thyroxine increased, Tri-iodothyronine increased.) • Arrhythmias^c • Cold or heat intolerance • Fatigue • Fever • Headache • Hypotension^c • Loss of appetite • Mental status and/or behavior changes • Nausea and/or vomiting • Unusual bowel habits • Vision disturbances • Weakness 	All attempts should be made to rule out other causes such as brain metastases, sepsis, and/or infection. An endocrinology consultation is recommended.
	Grade 3-4	Hold/discontinue MK-3475.	
 • Consider endocrine consultation. • Rule out infection and sepsis with appropriate cultures and imaging. • Treat with an initial dose of methylprednisolone 1-2 mg/kg IV followed by oral prednisone 1-2 mg/kg per day. When symptoms improve to grade 1 or less, steroid taper should be started and continued over no less than 4 weeks. Replacement of appropriate hormones may be required as the steroid dose is tapered. 		
Endocrine events 
 • Adrenal insufficiency • Hypophysitis • Pan-hypopituitarism 	Grade 1-4	Discontinue MK-3475.	
 • Thyroid hormone and/or steroid replacement therapy to manage adrenal insufficiency. • If Grade 1-2 hypophysitis is considered, pituitary gland imaging should be considered (magnetic resonance imaging [MRIs] with gadolinium and selective cuts of the pituitary can show enlargement or heterogeneity and confirm the diagnosis). • Grade 3-4 hypophysitis with clinically significant adrenal insufficiency and hypotension, dehydration, and electrolyte abnormalities (such as hyponatremia and hyperkalemia) constitutes adrenal crisis. Hospitalization and IV methylprednisolone should be initiated. 		

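### Section 6.1.2 gives opposite dosing orders for Grade 1-2 hypophysitis, and its Grade 3 colitis/diarrhea rule disagrees with Section 5.4

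*Combined protocol and SAP*

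**What the plan says.** **Hypophysitis.** Section 5.4, in its list of unacceptable adverse events, says "Hypophysitis or pan-hypopituitarism any grade should discontinue treatment". That line is nested under an item on Grade 3 or 4 laboratory abnormalities, which "do not require treatment discontinuation, with the following exceptions with approval of the Principal Investigator". The Section 6.1.2 table then covers hypophysitis in two endocrine rows:

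- The first row groups it with thyroid disorders and hypopituitarism. At Grade 1-2 the dose is unchanged and the action is "Monitor thyroid function or other hormonal level tests and serum chemistries more frequently until returned to baseline values". At Grade 3-4 the instruction is "Hold/discontinue MK-3475".
- The second row groups it with adrenal insufficiency and pan-hypopituitarism and stops the drug at Grades 1-4. Its action text includes "If Grade 1-2 hypophysitis is considered, pituitary gland imaging should be considered".

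**Colitis and diarrhea.** Section 5.4 says that a Grade 3 drug-related autoimmune or "inflammatory event including uveitis, pneumonitis, diarrhea, colitis, neurologic adverse events, hypersensitivity reaction, or infusion reaction of any duration requires discontinuation". In Section 6.1.2 the management cell for Grade 3-4 colitis/diarrhea withholds the drug and adds "Discontinue if unable to reduce corticosteroid dose to <10 mg per day prednisone equivalent within 12 weeks of toxicity". The action column of that row permanently discontinues Grade 3 enterocolitis.

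**Related text.** Section 5.1.1 allows restart after an adverse event that stopped treatment has resolved to Grade 1, with no exception for particular events. The introduction to Section 6.1.2 describes the table as guidelines subject to clinical judgment.

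**The concern.** A site with a Grade 1-2 hypophysitis case finds one cell telling it to keep dosing and another, in the same table, telling it to stop. A site with a Grade 3 colitis or diarrhea case finds a mandatory stop in Section 5.4 and a withhold-and-taper rule in Section 6.1.2. Following one written instruction would keep on drug, or re-dose, a patient whom another takes off drug.

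What is at stake is patient safety. The second endocrine row itself describes severe hypophysitis with clinically significant adrenal insufficiency as an adrenal crisis needing hospitalization, and Section 2.2.1.2 names colitis and diarrhea as important identified risks. A lesser consequence is that two sites could handle the same event differently, which would blur the discontinuation reasons (Section 13.5.3) and the exposure summaries (Section 13.11).

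**Working it through.** No arithmetic applies. The check sets the rules side by side and asks whether any other text reconciles them.

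**Step 1: hypophysitis, by grade**

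| Grade | 6.1.2, first endocrine row | 6.1.2, second endocrine row | 5.4 |
|---|---|---|---|
| 1-2 | Dose unchanged, monitor | Stop | Stop (any grade) |
| 3-4 | Hold or stop | Stop | Stop (any grade) |

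At Grades 1-2 the two rows are opposite. At Grades 3-4 the first row leaves a hold open and the second does not. The second row cannot be read as covering severe cases only, because it is labelled Grade 1-4 and its action text mentions Grade 1-2 hypophysitis. The contradiction therefore stands within the table, without help from Section 5.4. Section 5.4 then indicates the direction, and it agrees with the second row.

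**Step 2: Grade 3 drug-related colitis/diarrhea**

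| Event | 5.4 | 6.1.2 management cell | 6.1.2 action column |
|---|---|---|---|
| Grade 3 colitis or diarrhea | Stop, any duration | Withhold; stop if steroids are not reduced within 12 weeks | No permanent stop stated |
| Grade 3 enterocolitis | Stop, if read as an inflammatory event | Withhold; same condition | Permanent stop |

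For colitis and diarrhea the conflict is between the two sections. For enterocolitis the row also disagrees with itself.

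**Step 3: does other text settle it?**

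- The guideline wording in Section 6.1.2 allows judgment in applying a recommendation. It does not say which of two opposite cells is the recommendation. Section 5.1.1 also makes unacceptable adverse experiences a reason to stop by pointing to Section 6.1.
- The rechallenge sentence in Section 5.1.1 adds a third rule. It does not reconcile an unchanged dose with a stop, and as written it could reopen treatment after an event that another section treats as permanent.
- Section 6.1.1 opens by withholding for drug-related non-hematological toxicity of Grade 3 or higher. That leans towards the withhold cell for colitis/diarrhea, so the documents do not all point one way on that event.
- No sentence says whether Section 5.4 or Section 6.1.2 prevails.

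**Step 4: reach**

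The Study Summary reports the initial 26 patients and the additional 24 as enrolled, so 26 + 24 = 50. A correction can affect only those still on treatment (up to 24 months, Section 5.1.1) or retreated (up to 1 further year, Sections 5.1.1 and 5.10). The number is not given. Under Section 13.3.2, patients who stop for toxicity stay evaluable for response, so the ORR denominator and the Simon decision rule do not change.

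**The case against.** The strongest case on the other side is that the colitis/diarrhea cell may be the intended rule. It nearly repeats the general Grade 3-4 rule for immune-related events in Section 6.1.1, it fits the opening sentence of that section, and the rechallenge sentence permits restart. The Section 5.4 line could then be the outdated one, and a compulsory stop would take an option away from recovered patients with advanced cancer. This stands: the documents do not show which rule was meant. It is a reason for the sponsor to choose, not for leaving both rules in force.

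For hypophysitis, the Section 5.4 line sits awkwardly under a laboratory exception that mentions Principal Investigator approval. That weakens Section 5.4 as sole evidence, but the two table rows conflict without it. The guideline wording and completed enrollment also reduce the practical weight, without removing the contradiction.

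Three stronger readings are tempting and not supported:

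- *No rule stops Grade 4 colitis/diarrhea.* The list in Section 5.4 is open-ended and includes any patient needing systemic steroids. Section 6.1.2 treats Grade 3-4 diarrhea with intravenous steroids, so Section 5.4 read literally already reaches those patients.
- *Section 5.7 is a further stop rule for hypophysitis.* It says "Drug-related endocrinopathies (not including drug-related adrenal insufficiency or hypophysitis) adequately controlled with only physiologic hormone replacement may resume treatment". That withholds a permission to resume; it does not tell a site to stop a patient whose drug was never held.
- *The withhold cell is a copying error.* The similar wording in Section 6.1.1 is suggestive, but nothing in the documents establishes it.

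**Conclusion.** The table is wrong as written for hypophysitis: the orders are opposite at Grades 1-2 and differ at Grades 3-4, and Section 5.4 supports the row that stops treatment. For Grade 3 colitis/diarrhea, Sections 5.4 and 6.1.2 cannot both be followed when a patient's steroids can be reduced within 12 weeks, and the documents do not identify the intended rule.

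This should be fixed on patient-safety grounds. Its size cannot be stated as a number, because the documents do not say how many patients remain on treatment or may be retreated, and no event frequency is assumed here. A reader might infer that the efficacy result is compromised. The documents do not support that: neither the ORR analysis nor the error rates depend on these cells. The conclusion assumes only that the current text of Sections 5.1.1, 5.4 and 6.1.2 is in force together, with no stated precedence.

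**What to change.** 1. Delete hypophysitis from the first endocrine row of the Section 6.1.2 table so that the Grade 1-4 discontinue row governs. Check whether hypopituitarism should move too, since the second row and Section 5.4 name pan-hypopituitarism.
2. Choose one rule for Grade 3-4 colitis/diarrhea, covering enterocolitis, and state it identically in Sections 5.4 and 6.1.2. Discontinuation is the safer default and matches Section 5.4 and the enterocolitis text. If the sponsor prefers to withhold and taper, Section 5.4 and the enterocolitis sentence must change instead.
3. Add to the rechallenge sentence in Section 5.1.1 that it does not apply to events requiring permanent discontinuation.

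A blanket clause that Section 5.4 prevails is not advisable. Its systemic-steroid stop would override the resume rule for Grade 2 pneumonitis, and its Grade 3 line would override the taper rule for unlisted immune-related events.

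The cost is a few lines of text and a notice to sites. If discontinuation is chosen, a patient whose colitis or diarrhea resolves and whose steroids are reduced within 12 weeks could not resume. There is no change to sample size, endpoints or analysis.

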Additionally, immune-related adverse events (irAEs), defined as adverse events of unknown etiology, associated with drug exposure and consistent with an immune phenomenon, may be predicted based on the nature of the MK-3475 compound, its mechanism of action, and reported experience with immunotherapies that have a similar mechanism of action. Special attention should be paid to AEs that may be suggestive of potential irAEs. An irAE can occur shortly after the first dose or several months after the last dose of treatment. All AEs of unknown etiology associated with drug exposure should be evaluated to determine if they are possibly immune-related. If an irAE is suspected, efforts should be made to rule out neoplastic, infectious, metabolic, toxin or other etiologic causes prior to labeling an adverse event as an irAE.

The table below includes guidelines for managing irAEs that are not listed in the AE-specific table (see [section 6.1.2](#)).

General Dose Modification Guidelines for Drug-Related Immune-Related Adverse Events

irAE	Withhold/Discontinue MK-3475?	Supportive Care
Grade 1	No action	Provide symptomatic treatment
Grade 2	May withhold MK-3475	Consider systemic corticosteroids in addition to appropriate symptomatic treatment
Grade 3 and Grade 4	Withhold MK-3475 Discontinue if unable to reduce corticosteroid dose to < 10 mg per day prednisone equivalent within 12 weeks of toxicity	Systemic corticosteroids are indicated in addition to appropriate symptomatic treatment. May utilize 1 to 2 mg/kg prednisone or equivalent per day. Steroid taper should be considered once symptoms improve to Grade 1 or less and tapered over at least 4 weeks.

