Pneumonitis events 
 • Pneumonitis • Interstitial lung disease • Acute interstitial pneumonitis 	Grade 1	MK-3475 may be continued with close monitoring.	
 • Radiologic findings should be followed on serial imaging studies. • Consider pulmonary consultation and/or bronchoscopy if clinically indicated. 	Symptoms may include (but not limited to): 
 • Abnormal breath sounds • Chest pain and/or tightness^c • Dyspnea^c • Dry cough • Fatigue • Fever • Hemoptysis 	All attempts should be made to rule out other causes such as metastatic disease, bacterial or viral infection.
	Grade 2	Hold MK-3475	
To rule out other causes such as infection:
 
 • Consider pulmonary consultation with bronchoscopy and biopsy/bronchoalveolar lavage (BAL). • Consider pulmonary function tests. 
If the patient is determined to have study drug associated pneumonitis:
 
 • Treat with systemic corticosteroids at a dose of 1-2 mg/kg/day prednisone or equivalent. When symptoms improve to grade 1 or less, steroid taper should be started and continued over no less than 4 weeks. • Treatment with MK-3475 may be resumed if the event improves to ≤Grade 1 within 12 weeks and corticosteroids have been reduced to the equivalent of methylprednisolone 10 mg by mouth daily or less. Repeat chest imaging monthly as clinically indicated. 
For Grade 2 pneumonitis that improves to ≤Grade 1 within 12 weeks, the following rules should apply:
 
 • First episode of pneumonitis: May increase dosing interval by one week in subsequent cycles. • Second episode of pneumonitis: Discontinue MK-3475 if upon rechallenge the patient develops a second episode of ≥Grade 2 pneumonitis. 		

Event(s)	CTCAE v5.0 Grade	Management / Next Dose for MK-3475	Action / Supportive Care Guidelines	Symptoms ^a	Differential Diagnosis

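### Section 5.4 ends treatment for any need for systemic steroids, while Section 6.1 lets some steroid-treated patients resume, and nothing says which section governs

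*Combined protocol and SAP*

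**What the plan says.** Section 5.4 (Duration of Therapy) lets treatment run for up to 2 years or until a listed criterion applies. One criterion is an unacceptable adverse event. Two of the items under it matter here:

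- "Any patient requiring systemic steroid or other immunosuppressive treatment". No grade, dose or duration qualifies this.
- A separate item requires discontinuation for a Grade 3 drug-related autoimmune or inflammatory event, and names uveitis, pneumonitis, diarrhea and colitis among others.

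Two further items in 5.4 deal with restarting after steroids. The first begins "For patients with skin-only toxicity, when symptoms improve to Grade 1 or less, steroid taper should be started", sets the limit "Discontinue MK-3475 if unable to reduce corticosteroid dose for irAEs to ≤ 10 mg", and then allows restart. The second reads "Patients with peripheral thyroiditis and no other autoimmune/inflammatory event may be restarted after a short course of steroids on a stable replacement regimen".

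In Section 6.1.1, the general table for immune-related events (irAEs) withholds MK-3475 at Grades 3 and 4 under the rule "Discontinue if unable to reduce corticosteroid dose to < 10 mg per day prednisone equivalent within 12 weeks of toxicity". Section 6.1.2 carries the same rule in the Grade 3-4 colitis and diarrhea row. In the Grade 2 pneumonitis row, after systemic corticosteroids, "Treatment with MK-3475 may be resumed if the event improves to ≤Grade 1 within 12 weeks", provided that steroids are down to the "equivalent of methylprednisolone 10 mg by mouth daily or less".

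Section 5.1.1 separately allows rechallenge in patients stopped for an adverse event once it has resolved to Grade 1, and discontinues if the same event recurs at the same grade.

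**The concern.** Read literally, 5.4 ends treatment once systemic steroids are needed, unless the event is skin-only toxicity or peripheral thyroiditis. For several other events, 6.1 prescribes or contemplates systemic steroids and leaves the way back to MK-3475 open. Two sites could both follow the protocol and handle the same patient differently.

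The stop-or-resume decision bears on patient safety and also feeds reported quantities: the reason for discontinuation (13.5.3), exposure in cycles and dose intensity (13.11), and one PFS sensitivity analysis (13.5.1.2). If the decision depends on which section a site consulted, those quantities partly reflect site practice rather than the drug.

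**Working it through.** No arithmetic underlies the contradiction, so the check is to set the sections side by side.

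**Step 1. Stop or resume, event by event.**

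| Event | Section 5.4 | Section 6.1 | Result |
|---|---|---|---|
| Grade 2 pneumonitis | Ends treatment once systemic steroids are needed | Hold, give systemic steroids, may resume | Conflict |
| Grade 2 enterocolitis lasting over one week | Same | Systemic steroids; row says hold to Grade 1 or less, then resume; no steroid limit | Conflict |
| General irAE, Grade 3-4 | Ends treatment under the steroid bullet and, at Grade 3, also under the Grade 3 bullet | Steroids indicated; withhold; discontinue only if the steroid cannot be reduced | Conflict |
| Colitis or diarrhea, Grade 3-4 | Same | Management column withholds; supportive-care column permanently discontinues Grade 3 enterocolitis | Conflict, and the row disagrees with itself |
| Renal and Other events, Grade 3-4 | Ends treatment under the steroid bullet | Management column discontinues; supportive-care column allows restart | Row disagrees with itself |
| Grade 3 pneumonitis, Grade 3 uveitis | Ends treatment | Discontinue | Agreement |

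Hypophysitis is also stopped at any grade by 5.4 and by its dedicated endocrine row in 6.1.2. It appears as well in the other endocrine row, where Grade 1-2 carries no dose change; that is a separate matter.

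**Step 2. The steroid limits.**

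| Where | Limit | Reference steroid | Time window |
|---|---|---|---|
| 6.1.1 general irAE and 6.1.2 colitis/diarrhea, Grade 3-4 | Below 10 mg per day | Prednisone | 12 weeks |
| 6.1.2 pneumonitis, Grade 2 | 10 mg daily or less | Methylprednisolone | 12 weeks, attached to improvement of the event |
| 5.4 skin-only; 6.1.2 renal and Other events, Grade 3-4 | 10 mg or less | None named | None |

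Only the pneumonitis limit is worded as a condition for resuming. The others are conditions for discontinuing, so resumption follows by implication or from an adjacent restart sentence. The protocol gives no conversion between the two named steroids.

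**Step 3. Is there a governing section?** The cross-references point both ways. Section 5.1.1 refers unacceptable adverse experiences to 6.1, while 5.6 refers removal criteria to 5.4. Section 5.7, on resuming treatment, is introduced for events that are not autoimmune or inflammatory and gives no steroid limit. Section 5.3.1 exempts steroids for suspected immune events from its prohibited list, which fits 6.1 better than the unqualified 5.4 bullet.

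**Step 4. Effect on the analysis.** Patients who stop for toxicity remain evaluable for response (note in 13.3.2), and the ORR denominator is eligible patients with at least one dose (13.5.1.1). It does not move. The PFS sensitivity analysis in 13.5.1.2 treats a patient without documented progression or death who discontinued treatment as progressed, at the later of discontinuation or new therapy. A patient stopped under 5.4 would be an event there; the same patient resumed under 6.1 would stay at risk. If all 50 patients are in the efficacy population, one such patient is 1/50 = 2% of it.

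**The case against.** The best defence is that 5.4 says when dosing stops, while 5.1.1 and 6.1 say when it may restart. The steroid bullet does not say that the stop is permanent, and 5.1.1 has a general rechallenge sentence. This reading is possible and softens the conflict, but it does not settle it. Section 5.4 does not refer to the rechallenge sentence, and its own restart text for two event types would be largely unnecessary if a general restart rule already applied. The 5.1.1 condition is resolution to Grade 1 with no steroid limit, which does not match 6.1. Nor does the reading cover Grade 2 renal and Other events, where 6.1.2 says that steroids may be indicated but only suggests considering withholding.

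Section 6.1.2 also describes itself as guidelines subject to clinical judgment. That is true, but it does not say that 5.4 prevails. Accrual was complete by this version, which limits the consequence; still, treatment can run 24 months with up to a further year of retreatment, and the rules also determine how past discontinuations are classified.

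Four stronger readings are tempting, and the documents do not support them:

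- A reader might infer that every patient given steroids for a non-skin, non-thyroid event is affected. Step 1 shows events that both sections stop.
- A reader might infer that most immune-related events need systemic steroids. The protocol gives no proportion, and many lower-grade rows call only for monitoring, topical or symptomatic care.
- A reader might infer that a patient on exactly 10 mg prednisone passes one limit and fails another. The general table covers only events absent from the AE-specific table, and no row of the latter carries two different numerical limits. The limits differ between events; they are not shown to give one event two answers.
- A reader might infer that a single limit is needed throughout. Event-specific limits may be intended.

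**Conclusion.** The point holds and the text is wrong as written. Sections 5.4 and 6.1 give opposing instructions for Grade 2 pneumonitis treated with steroids, persistent Grade 2 enterocolitis, general Grade 3-4 irAEs and Grade 3-4 colitis or diarrhea. At Grade 3 the conflict has two sources in 5.4, so amending the steroid bullet alone would leave half of it in place. Three rows of 6.1.2 (Grade 3-4 colitis/diarrhea, renal, Other events) are also internally inconsistent, and two of the three forms of steroid limit leave a reference steroid or time window unclear.

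The effect is on safety management, exposure, discontinuation reasons and one PFS sensitivity analysis, not on the ORR denominator. Its size depends on how many patients had these events and needed systemic steroids, which the sections compared here do not give; 2% per patient assumes an efficacy population of 50. The conclusion rests on reading the 5.4 list as criteria that end treatment, which is how its lead-in presents it.

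**What to change.** Amend the text so that:

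1. Both 5.4 bullets, the one on systemic steroids and the one on Grade 3 autoimmune or inflammatory events, are reconciled with 5.1.1, 6.1.1 and 6.1.2, with every exception listed.
2. One sentence states which section governs when they differ, and whether the 5.1.1 rechallenge sentence applies to stops under 5.4.
3. The Grade 3-4 colitis/diarrhea, renal and Other events rows each give one instruction.
4. Each steroid limit names its reference steroid and its time window, and the sponsor confirms whether differences between events are intended.

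Which clinical rule and which limits apply is for the sponsor's clinicians. The cost is amendment wording and notice to sites; no change to sample size, endpoints or data collection is needed.
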